#### Short term assessment neurological evaluation will include:

- 1) Time to recovery after birth of a normal aEEG [1]
- 2) MRI scan before 14 days of life [33, 2, 44]
- 3) Peak LDH value within 72h of life [4, 34]

We will also collect data on:

- 4) First plasma glucose after birth (usually from cord blood)
- 5) Age in hours after birth when plasma lactate has declined to <5mmol/l
- 6) Number and type of inotropic drugs needed during stay on the neonatal intensive care unit (typically the period from birth to 3-5 days of age) and the total duration in hours of any inotropic support
- 7) Number of anticonvulsant drugs given during stay on the neonatal intensive care unit.
- 8) Amount and duration of sedation (eg morphine) while ventilated mechanically on the neonatal intensive care unit.
- 9) Age at full oral feeds (breast or bottle or tube)
- 10) Outcomes of neonatal hearing screening before 14 days of life
- 11) Clinical examination at birth, at 7 days of age and at discharge including weight and head circumference

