**Secondary Objectives:**

We will monitor a number of variables before/during and after the period of xenon delivery. This group of physiological and biochemical parameters includes those recorded during our recently completed xenon+cooling feasibility/safety study in neonates and a few more are added .

They are:

Gas exchange: Transcutaneous oxygen saturation, end-tidal carbon dioxide concentration, blood gas data (from arterial sample), mechanical ventilation requirements (rate, peak inspiratory pressure, PEEP settings).

Haemodynamic: Systolic, mean and diastolic arterial pressure, heart rate.

Any problems during weaning and extubation, such as post-extubation stridor, use of steroids.

We have also looked at other variables in the infants cooled in our hospital (inborn or outborn) ca 30/year since 1/12/06. We chose the best matched controls (3:1) from this cooling database and compared them with the 14 infants in the recent Xenon + cooling human feasibility study (the precursor to this study),

We will also record:

- 1] Coagulopathy [INR >2, APTT> 50]
- 2] Inotrope requirement, cardiac Troponin T
- 3] Hepatic impairment, [raised Alanine aminotransferase > 40, Alkaline phosphatase > 100, peak Lactate dehydrogenase within 72h of age
- 4] Renal impairment, oliguria [urine output < 1 ml/kg/h after day 1 of life and raised creatinine > 100]
- 5] Infection [culture proven, need for antibiotics  $\geq$  5 days, raised CRP  $\sim$  within the first 24h and at 4 days of life of life]
- 6] Number of anticonvulsive drugs needed to treat seizures
- 7] Length of hospital stay
- 8] Time to full oral feed by bottle or breast
- 9] MRI assessment by T1 and T2 weighted images using the scoring system by Rutherford et al [2].
- 10] In some infants when the 3Tesla MRI scanner is available assessment of brain metabolites using magnetic resonance spectroscopy (MRS) where the ratio Lactate/N-acetyl aspartate has

Reference:	CH
Issue:	2
Revision:	3
Issue Date:	1 May 2013
Page	5 of 49

	been shown to be a good early biomarker for outcome [5].  Safety

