#### St Michael's hospital standard inclusion criteria for cooling:

Standard Hypothermia Treatment Criteria for 72 hrs of cooling — all of criteria A, B, and C.

A Infants  $\geq$  36.0 weeks gestation (estimated or clinical assessment) with at least ONE of the following:

- 1 Apgar score of  $\leq$  5 at ten (10) minutes after birth
- 2 Continued need for resuscitation, including tracheal or mask ventilation, at ten minutes after birth
- 3 Acidosis defined as either umbilical cord pH or any arterial, venous or capillary pH within 60 minutes of birth less  $<$  7.00
- 4 Base deficit  $\geq$  16 mmol/L in umbilical cord blood sample or any blood sample within 60 minutes of birth (arterial or venous blood). If the infant meets criterion A then assess for neurological abnormality using criterion B and C (by trained personnel):

B Moderate or Severe encephalopathy as evidenced by any of the following --

- 1 Altered state of consciousness (reduced or absent responses or pathological irritability and hyper responsive and at least ONE or more of the following:
- 2 Hypotonia
- 3 Abnormal reflexes including oculomotor or pupillary abnormalities
- 4 Absent or weak suck
- 5 Clinical seizures, as recorded by trained personnel

*And*

C At least 30 minutes duration of amplitude-integrated electroencephalography (aEEG) recording that shows abnormal background aEEG activity. The decision to cool is based on the worst 30 min section of the aEEG, not the best [35] or seizures (clinical or electrical) thus meeting ONE of the following:

- 1 Normal background with some ( $>$  5 min) electrical seizure activity
- 2 Moderately abnormal activity (upper margin of trace  $>$  10  $\mu$ V and lower margin  $<$  5  $\mu$ V)
- 3 Suppressed activity (upper margin of trace  $<$  10  $\mu$ V and lower margin of trace  $<$  5  $\mu$ V)
- 4 Definite seizure activity

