#### Additional inclusion criteria for xenon

Before being considered for additional inhaled xenon therapy via the breathing gas mixture, the infant would need to meet further additional entry criteria (all must be met):

- 1) Intubated, ventilated, sedated, being cooled.
- 2)  $<$  5 hours old
- 3) Any seizures under control.
- 4) Weight  $>$  2nd centile for gestational age
- 5) Stable cardiovascular parameters; Mean arterial pressure  $>$  40 mmHg.
- 6) Oxygen requirement via mechanical ventilator  $<$  40%.
- 7) Positive End Expiratory Pressure (PEEP) requirement  $<$  6 cm H2O
- 8) Arterial/capillary/venous pCO2  $<$  7.0 kPa (ideally arterial). Venous can be higher if peri-arrest and tissues have been very recently ischaemic
- 9) Postnatal age  $<$  5 hours
- 10) Absence of major congenital abnormalities, imperforate anus and in particular any bowel obstruction, congenital abnormalities suggestive of chromosomal anomaly or other syndromes that include brain dysgenesis. Congenital syndromes affecting the brain should be excluded when diagnosed.

Reference:	CH
Issue:	2
Revision:	3
Issue Date:	1 May 2013
Page	17 of 49

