#### **5.1 Inclusion Criteria**

Patients meeting the following criteria will be considered eligible for the study:

Infants will be eligible for inclusion in this study if the St Michael's hospital standard inclusion criteria for cooling are met and additional inclusion criteria for xenon administration are met.

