## 7.5 Study Phases

The study consists of:

### 7.5.1 Phase 1

Identification of potential subjects – initially using same identification method used in St. Michael's Hospital Bristol to identify infants who would benefit from cooling.

Compliance with all inclusion/exclusion criteria for use of xenon in addition to cooling (the standard treatment).

### 7.5.2 Phase 2

Formal recruitment, information supplied to / discussions with parents.  
Consent.

### 7.5.3 Phase 3

Completion of all screening / demographics / baseline data collection immediately pre-xenon, reintubation with cuffed tube, x-ray for tube placement and blood gas

Administration of 50% xenon for 18 hours to infant according to randomisation protocol.

Completion of all data collection, serum chemistry and examinations immediately post-xenon and post-cooling.

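### The anticonvulsant count and the aEEG seizure measure do not start at randomisation, so events before allocation add noise to the between-arm comparison

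*Protocol*

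**What the plan says.** **The count.** Section 3.2, in the list of short-term neurological evaluations, has as item 7 the "Number of anticonvulsant drugs given during stay on the neonatal intensive care unit". Section 7.5.4 repeats it. Item 6, on inotropes, uses the same term for the stay and explains it as "typically the period from birth to 3-5 days of age". The Protocol Summary (Secondary Objectives, item 6) lists the "Number of anticonvulsive drugs needed to treat seizures" without a window, and section 2.1 also lists the count without one.

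**Seizures on aEEG.** Item 8 of the pre-discharge list in 3.2 (and 7.5.4) has aEEG recorded continuously until after rewarming, with seizure occurrence and duration assessed. No start at allocation is given.

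**Entry.** Under the cooling criteria in 3.1, B5 is "Clinical seizures, as recorded by trained personnel". Criterion C is satisfied by "thus meeting ONE of the following", and two of its four options (C1 and C4) are seizure activity. The additional criteria for xenon include "Any seizures under control". Section 5.1 makes an infant eligible for the study when the cooling criteria "are met and additional inclusion criteria for xenon administration are met".

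**Recording.** Endpoint 12 (section 2.2) has the aEEG pattern, seizures and anticonvulsant treatment recorded before, during and after xenon, up to 12 h after cooling ends. Section 7.4.3 records a start date, and a stop date where applicable, for each concomitant drug.

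**Analysis.** Section 9.1 is descriptive. It compares the two groups of 16, estimates differences, and also compares with 45 historical cooled infants.

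**The concern.** A measure meant to show a difference between xenon plus cooling and cooling alone is most informative when it counts only what happens after allocation. Here an infant can qualify on seizures, receive one or more drugs to control them, and only then be randomised. Those drugs still count towards the whole-stay total, and a seizure on the entry aEEG already makes seizure occurrence positive.

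An example shows the loss. Infant A receives two drugs by 3 h, is then randomised and needs none afterwards. Infant B receives none before entry and two after allocation. Both score 2, although only B's score could have been influenced by the allocated treatment.

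At stake is the precision and interpretability of a supporting comparison in a small pilot. With 16 per arm, a chance difference in how many infants arrive already treated passes directly into the estimated difference in the count.

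**Working it through.** **1. Order of events.** Section 7.5.1 (Phase 1) requires "Compliance with all inclusion/exclusion criteria for use of xenon in addition to cooling (the standard treatment"). Information and consent follow in Phase 2, and xenon according to randomisation in Phase 3. The flow chart in 3.0 has the same order. With section 5.1, this means seizure control is a condition for both arms before allocation. That control was achieved with a drug is an inference; it will hold in some infants and not in others.

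**2. Does another part of the protocol supply the cut?**
- Endpoint 12 divides time around xenon. The cooling-only arm has no xenon period, so the division is undefined there. Its window also ends 12 h after cooling, which differs from the NICU stay.
- Section 7.4.3 asks for dates, with no time of day. Xenon must start within 5 h of birth, so drugs given before and after allocation will often carry the same date.

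**3. Effect on the count.** The protocol states no rate, SD or effect for this variable, so there is no figure to reproduce. Write total = pre + post, where post is the number of drugs newly started after allocation. With 1:1 allocation the expected pre count is equal in the two arms, so the expected difference in mean total equals the expected difference in mean post. Only the variance grows. With r = SD(pre)/SD(post) and ρ their correlation, the share of the standardised effect retained is

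1/√(1 + r² + 2ρr)

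| r (assumed) | ρ = 0 | ρ = 0.3 | ρ = 0.6 |
|---|---|---|---|
| 0.5 | 0.89 | 0.80 | 0.74 |
| 1.0 | 0.71 | 0.62 | 0.56 |

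If infants already treated tend to start fewer new drugs, ρ is negative and the loss is smaller; at ρ = −r/2 the formula gives 1, i.e. no loss.

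**4. A concrete version.** Assume a share q of infants is treated before allocation, 70% of them with one drug and 30% with two, and an independent Poisson post count with mean 0.6. Among the treated, the mean is 0.7 × 1 + 0.3 × 2 = 1.3 and the mean square is 0.7 × 1 + 0.3 × 4 = 1.9. So Var(pre) = 1.9q − (1.3q)², and the SE of the arm difference grows by √((0.6 + Var(pre))/0.6). The SE of the chance imbalance in mean pre count between arms is √(2 Var(pre)/16).

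| q (assumed) | Var(pre) | SE ratio | SE of chance imbalance (drugs per infant) |
|---|---|---|---|
| 0.2 | 0.312 | 1.23 | 0.20 |
| 0.4 | 0.490 | 1.35 | 0.25 |
| 0.6 | 0.532 | 1.37 | 0.26 |

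For scale, the SE of the difference in the post count alone is √(2 × 0.6/16) = 0.27.

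**5. Effect on a yes/no seizure measure.** An infant with a seizure before allocation is positive in either arm. If xenon acts equally in infants with and without entry seizures, and q is now the share with a seizure before allocation, the observed risk difference is (1 − q)(p₀ − p₁). With assumed risks after allocation of 40% and 20%, this is 16, 12 or 8 points at q = 0.2, 0.4 or 0.6, instead of 20. Here the expected difference itself shrinks, unlike the mean count.

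**The case against.** Several arguments on the other side carry weight.

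- **Counting windows for supporting variables usually belong in the SAP, which is not at hand.** This stands as to where the remedy may be written. It does not remove the point, because item 7 does state a window, and the only division by period that the protocol offers cannot be applied to the control arm.
- **The protocol already collects most of what is needed.** True: Endpoint 12 and the dated drug record allow most of the separation. What is missing is a cut point common to both arms and a dose time on the day of birth.
- **The variable is minor.** True. In 2.1 and 3.2 the count is additional data, outside the main analysis of aEEG recovery, MRI and LDH, and section 2.0 does not name it among the biomarkers compared. Section 9.1 says the study lacks power to test outcome.
- **The window from birth is partly inferred.** Also true. The explanation stands under the inotrope item, with a qualifier. But a stay on the unit, however dated, does not begin at allocation.
- **The magnitudes rest on assumptions.** Agreed. In addition, no measure of any anticonvulsant use, yes or no, is a protocol outcome, so the yes/no attenuation concerns only aEEG seizure occurrence.
- **Replacing the total would harm the comparison with the 45 historical infants**, for whom the protocol gives no randomisation time. This stands, and is why the total should be kept.

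A reader might infer that the whole-stay count biases the comparison for or against xenon. The documents do not support that: allocation is random and the entry criteria are the same for both arms.

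**Conclusion.** The point holds as a minor one. Part of the anticonvulsant count and of aEEG seizure occurrence can be fixed before randomisation, and the protocol gives no cut point that works in both arms. For the mean count, the consequence is extra variance and chance imbalance with 16 per arm, without systematic bias. For a yes/no seizure measure, it is attenuation.

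The size is not derivable from the protocol. Over the assumed range (r from 0.5 to 1, ρ from 0 to 0.6) the count loses 11% to 44% of its standardised effect. These figures depend on inputs that the protocol does not give, and the loss would be less if drugs before and after entry were negatively correlated.

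It would go too far to say that every infant carries a pre-allocation component, since seizures are one alternative among several under both B and C. Nor does the point touch the main analysis or the feasibility aim.

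**What to change.** In 3.2 and 7.5.4, or in the SAP, make these changes:

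1. For the between-arm comparison, report the number of anticonvulsants started after randomisation, and aEEG seizure occurrence and duration counted from randomisation. Use the same clock in both arms.
2. Show anticonvulsants and seizures before randomisation by arm, as baseline.
3. Keep the whole-stay total, labelled as such, for comparison with the historical cooled infants.
4. State how Endpoint 12's periods apply in the cooling-only arm, or replace the xenon reference there with randomisation.

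The cost is small. The aEEG and drug start dates are already collected; the CRF needs the time of the first dose on the day of birth, and the report needs one extra summary. No treatment changes. One limitation remains: a drug started before entry and given again later is not new, so an infant already treated can score 0 where an untreated infant with the same later seizure scores 1. The baseline display must therefore be read together with the count.

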#### Long term follow up (at 18 months)

Reference:	CH
Issue:	2
Revision:	3
Issue Date:	1 May 2013
Page	24 of 49

Neurodevelopmental follow up is a part of the routine follow up of infants with Neonatal Encephalopathy. Bayley II examination at 18 months of age is used to compare the results from this study with our large local patient database and previous randomised controlled trials (CoolCap, Gluckman 2005; TOBY, Azzopardi 2009) [10, 11] where Bayley II was also used: we were a main recruiting centre for these trials.

Disability will be defined as any of:

Bayley II mental developmental scale score (MDI) less than 70.

Bayley II motor development scale score (PDI) less than 70. MDI and PDI will also be calculated as developmental quotients (DQ), as this allows a larger range of score for those functioning at a low level [35]. Bilateral cortical visual impairments.

Hearing loss needing amplification > 40 DB.

#### **Additionally:**

We will do both short-term (14 days) and long-term (18 months survival) follow-up. In cooled babies we have shown that short-term predictors such as MRI at day 8 [2], time to normal aEEG [1] and peak LDH before 72h [4] predict long-term outcome with a positive predictive value of 84%, 92% and 80% respectively. In this study we will be able to examine these predictors for cooled babies receiving xenon treatment. By defining this relationship one can calculate the sample size for a large trial using short-term outcome.

### **3.3 Justification of Design**

A human neonatal randomised pilot study comparing cooling (the established treatment) with the cooling+50% xenon combination is now the next logical step (see “Justification of Treatment” 3.4 below). This study is necessary for 3 reasons:

- 1) To validate our ability to recruit a large proportion of infants needing cooling as early as 3h of age and start xenon by 5hrs.
- 2) To examine the positive predictive value of our early outcome biomarkers proposed from the previous 100 cooled babies and compare with these.
- 3) Use these data for the statistical power calculations to estimate the group sizes for a larger randomised clinical trial of cooling+xenon. This approach follows a similar pattern to the early studies of cooling in neonates; a human technical feasibility/safety study [42] was performed using different target temperatures, followed by a study using a fixed temperature protocol for 72hours [20]. This protocol was then used in CoolCap [10], modified slightly for NICHD (National Institute of Child Health and Human Development)[43] and again used in TOBY, which were the 3 first large randomised controlled cooling trials. [12]

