## Protocol Summary

Title	XENON AND COOLING THERAPY IN BABIES AT HIGH RISK OF BRAIN INJURY FOLLOWING POOR CONDITION AT BIRTH: RANDOMISED PILOT STUDY (COOLXENON2 STUDY)
Investigators	[name] (Chief Investigator) e-mail: [contact] Mob: [name] [name] (Co-Investigator) e-mail: [contact] Mob: [name] [name] (Co-Investigator) e-mail: [contact] Mob: [name] [name] (Co-Investigator) [name] (Co-Investigator) [name] (Co-Investigator) [name] (Co-Investigator) [name] (Co-Investigator) [name] (Co-Investigator) [name] (Co-investigator)
Study Centre	St Michael's Hospital [name]
Test Article	Xenon Neonatal Breathing Device
Objectives	
Primary Objective: This is a randomised two group pilot study comparing:
 
 
i) xenon inhalation for 18 hours in combination with whole body cooling to 33.5 °C for 3 days, to
 
ii) the established treatment of cooling the body down to 33.5 °C for 3 days.
 
 
This will be applied in term newborn babies who are at moderate or high risk of brain injury following poor condition around the time of birth.
 
Our hypothesis is that during the first 2 weeks after birth using a combination of validated (in our own and others cohorts) early predictors of outcome we may observe an enhanced neuroprotective effect of the xenon-cooling combination over cooling alone and this will allow us to perform power calculations for a larger definitive neurological outcomes study of otherwise similar design.
 
Outcome predictors are based on a combination of:
 
 
1) Time in hours after birth when background activity as recorded by amplitude integrated EEG (aEEG: from single channel EEG) [1] and
 

Reference:	CH
Issue:	2
Revision:	3
Issue Date:	1 May 2013
Page	4 of 49

onset of sleep wave cycling (SWC). Time to Normal trace and SWC are both very good (PPV>90%) outcome predictors  
 2) MRI before 2 weeks of age (T1W and T2W) has a PPV of 84% in cooled infants in the TOBY trial in which we were a major recruiting centre [2] Resistance Index (RI) was not a definite predictor for cooled infants [3]). We will do the examination but not use it in the prediction. Peak value of Lactate Dehydrogenase within the first 72h of life [4, and [name] M 2012 submitted ].

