## 2.0 Objectives

The aim of this study is to examine using primarily short term measures and secondarily long term outcomes, the potential neuroprotective effects of the cooling+xenon combination when compared to cooling alone. We will examine the feasibility of recruiting earlier than previous trials, <3h for HT and <5h for starting xenon and assess what proportion of the eligible infants we can recruit. We will compare the short term biomarkers (aEEG recovery, MRI score, LDH and time to full feeds) in the two groups with those obtained previously in our randomised dataset (infants from CoolCap and TOBY) as well as the large group cooled since 1/12/2006 under the same protocol. In these groups of children we have both short term markers as well as Bayley outcome and have shown that our combined biomarkers has a PPV of 93%.

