### Primary Objective:

This is a randomised two group pilot study comparing;

- i) Adding xenon inhalation for 18 hours in combination with the (existing) whole body cooling to 33.5 °C for 3 days.
- ii) The established treatment of cooling the body down to 33.5 °C for 3 days.

This will be applied in term newborn babies who are at moderate or high risk of brain injury following poor condition around the time of birth, the purpose being to reduce long term neurological impairment resulting from their condition.

Our hypothesis is that early predictors of outcome\* will show a trend towards an enhanced neuroprotective effect of the xenon-cooling combination over cooling alone. The early predictors will allow us to perform power calculations for a much larger neurological outcomes study of otherwise similar design.

In addition we will examine the feasibility of earlier recruitment and start of xenon and whether we obtain the same early predictor data in the hypothermia-only group as we have in our previous hypothermia database.

(\*the total clinical follow up period will be much longer than this as is already the case for cooled babies in Bristol)

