## 2.1 Primary Endpoint

This is a randomised two group pilot study comparing;

- 1) xenon inhalation for 18 hours in combination with whole body cooling to 33.5 °C for 3 days, to
- 2) the established treatment of cooling the body down to 33.5 °C for 3 days.

Reference:	CH
Issue:	2
Revision:	3
Issue Date:	1 May 2013
Page	13 of 49

This will be applied in term newborn babies who display signs indicating moderate or severe brain injury following poor condition at birth.

Our hypothesis is that we may observe an enhanced neuroprotective effect of the xenon-cooling combination over cooling alone assessed initially by early outcome predictors. This will allow us to perform power calculations for a much larger neurological outcomes study of otherwise similar design. We have tested a combination of our early predictors (using our TOBY registry cooling data in 80 infants) against Bailey outcome at 18 months and found they have a positive predictive value of 94% in cooled infants

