**Eligibility**  
 Meet inclusion and exclusion criteria  
 This includes  
 ≥36.0 weeks gestational age  
 Expectation of being able to start cooling at ≤3h age and, if required  
 Xe at ≤5h age.

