## 9.0 Data Analysis and Statistical Plan

### 9.1 Statistical Analysis

This is a randomised pilot study. Data presentation will include descriptive statistics only. These will be compared in the 2 treatment groups but also to recordings of the same variables in a similar group of 45 infants (recruited to cooling only from the same entry criteria) recently treated in our department (historical control data). Differences between the groups will be estimated

Sample size is 16 infants in each group. In accordance with the paper by Julius (Appendix 11), 12 is a large enough number to estimate the mean value of short term outcome variables for the group. The study does of course not have the power to test outcome. The main purpose of this randomised pilot study is to examine whether early recruitment is feasible, secondly whether the short term biological markers show the expected range of values in the cooled only group as compared to our historical controls. Our advisory statistician for this study is [name] who also advised all our experimental xenon work as well as the recent clinical feasibility study.

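### Feasibility of early recruitment is the stated main purpose but is not among the endpoints; its denominator and the late-cooling cut-off vary between sections, and 16 xenon infants cannot supply a predictor relation for sizing a large trial

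*Protocol*

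**What the plan says.** **Main purpose.** Section 9.1, and the Statistical Analysis row of the Protocol Summary in the same words, state: "The main purpose of this randomised pilot study is to examine whether early recruitment is feasible". Section 2.0 opens differently: "The aim of this study is to examine using primarily short term measures and secondarily long term outcomes, the potential neuroprotective effects". It turns to feasibility in its next sentence. The Primary Objective gives the neuroprotection hypothesis first and then continues: "In addition we will examine the feasibility of earlier recruitment and start of xenon". Section 2.1, headed Primary Endpoint, says "we may observe an enhanced neuroprotective effect of the xenon-cooling combination over cooling alone assessed initially by early outcome predictors" and names aEEG recovery, MRI and peak LDH for the main analysis. It contains no recruitment measure. The Summary objective also leads with neuroprotection: "we may observe an enhanced neuroprotective effect of the xenon-cooling combination over cooling alone and this will allow us to perform power calculations".

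**Denominator.** Section 3.3, reason 1, refers to all infants who need cooling ("To validate our ability to recruit a large proportion of infants needing cooling as early as 3h of age and start xenon by 5hrs"). Section 2.0 says the study will "assess what proportion of the eligible infants we can recruit". The group-size text in 3.3 refers to consecutive babies who meet the entry criteria. Timing is part of those criteria. The eligibility box in 3.0 lists "Expectation of being able to start cooling at ≤3h age and, if required", followed by xenon by 5 h, and the xenon inclusion lists in 3.1 and 5.1 require an age under 5 h.

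**Late cooling.** The cooling exclusion applies to infants expected to be older than 3 h in section 3.1, and older than 5 h in section 5.2.

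**Predictor relation.** Sections 3.2 and 7.5.4 say the early predictors will be examined in cooled babies who receive xenon, and that defining the relation to long-term outcome allows a large trial's sample size to be calculated.

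**The concern.** A pilot is judged on its main purpose. Here sections 9.1 and 2.1 would lead a reader to judge it on different results, and the one called main has no place among the endpoints.

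The denominator matters because the Summary and the group-size text in 3.3 justify 8 additional babies by infants lost to the time limit before xenon could be started during transport. A proportion that can be read as leaving those infants out may understate the very loss that the extension is meant to address.

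The two late-cooling cut-offs affect who enters and who counts as eligible. The sample-size sentences promise a use of the data that the size of the xenon arm does not support.

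**Working it through.** **1. The plan's own sample size.** The 12-per-group rule plus 8 babies gives 2 × 12 + 8 = 32 = 2 × 16, as stated. The rule concerns precision of a mean or variance. The 95% half-width of a group mean, t(0.975, n−1)/√n, is 0.64 SD at n = 12 and 0.53 SD at n = 16. This says nothing about the precision of a predictive value.

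**2. Late-cooling cut-offs side by side.**

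| Place in the protocol | Limit for starting cooling |
|---|---|
| Summary (Patient Population), Overview, eligibility box in 3.0 | 3 h |
| 3.1, exclusion for cooling | excluded if expected after 3 h |
| 3.1, Randomisation and Clinical management | 3 h |
| 5.2, exclusion for cooling | excluded if expected after 5 h |

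An infant expected to be first cooled between 3 and 5 h is excluded by 3.1 and not by 5.2.

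**3. Recruitment by April 2013.** The Summary gives 8 + 7 = 15 recruited. It says about the same number were missed for time, which can be read as about 15 or about 7. Section 3.3 likens the number missed to the number recruited to xenon, which supports about 7. Intervals are exact (Clopper-Pearson) 95%, and no other losses are assumed.

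| Count | Proportion | 95% CI |
|---|---|---|
| About 7 missed, counted as not recruited | 15/22 = 68% | 45 to 86% |
| About 15 missed, counted as not recruited | 15/30 = 50% | 31 to 69% |
| All time-missed infants dropped (upper extreme) | 15/15 = 100% | 78 to 100% |

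Other losses are not reported. With about 7 missed for time and r other losses assumed, the comparison is 15/(22 + r) against 15/(15 + r):
- r = 0: 68% against 100%
- r = 5: 56% against 75%
- r = 10: 47% against 60%

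The gap therefore runs from 32 down to 13 percentage points.

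**4. Predictive value in the xenon arm.** The inputs are 16 xenon infants (3.3), a poor-outcome rate under cooling of 39% (1.2) to 51% (3.4), and cited predictive values of 84%, 92% and 80% (3.2). Assume predictors split into positive and negative, with about as many positives as poor outcomes. Then 16 × 0.39 = 6.2 and 16 × 0.51 = 8.2, so about 6 to 8 positives. Exact 95% intervals:
- 5/6: 36 to 99.6%
- 6/7: 42 to 99.6%
- 7/8: 47 to 99.7%

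All three contain 80%, 84% and 92%. As a bound, if all 16 were positive and all had a poor outcome, the lower limit would be 0.025^(1/16) = 79%, still below the lowest cited value.

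**5. What that does to a large trial (illustration only).** Assume predictor-positive rates q of 40% and 25%, a negative predictive value of 0.90, two-sided 5% and 80% power. The poor-outcome rate is q × PPV + (1 − q) × 0.10. The standard two-proportion formula then gives:
- PPV 0.84: 39.6% against 28.5%, 285 per arm
- PPV 0.42: 22.8% against 18.0%, 1106 per arm
- PPV 0.99: 45.6% against 32.3%, 209 per arm

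The last two values lie close to the ends of the 6/7 interval.

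**The case against.** **Denominator.** A reader might infer that the wording in 2.0 and in the group-size text removes every time-missed infant, so that the proportion must be 100% before and after the transportable system. The documents do not support that. The eligibility box in 3.0 and the exclusion in 3.1 turn on expectation, so an infant expected to be in time who then missed the window stays eligible and counts as not recruited. The age limit of 5 h applies when the infant is considered for xenon, and an infant still at a referring hospital may meet it. The Summary and 3.3 also make the intent clear: missed infants are treated as recruitment failures. What stands is that the wording permits a reading that drops some or all of them, and that the 100% is an extreme.

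**Aims.** Section 2.0 does not omit feasibility, reason 1 in 3.3 puts it first, and section 9.1 limits the analysis to description. No test depends on the order. The gap in 2.1 remains.

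**Late cooling.** A reader might infer that an infant first cooled at 3 to 5 h is at once excluded and eligible. That goes too far: passing 5.2 does not satisfy the eligibility box, which expects cooling by 3 h. The two exclusion lists still disagree.

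**Predictors.** Sections 3.2 and 7.5.4 speak of a trial using short-term outcome. Such a trial could be sized on marker means and variances, which reason 3 in 3.3 covers and which is not disputed. But both sentences name the relation to long-term outcome as what makes the calculation possible, and that relation is the imprecise quantity.

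**SAP.** Operational detail may be left to an SAP. The conflicting statements are in the protocol itself.

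**Conclusion.** The point holds in four limited parts, and an amendment is worthwhile.

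- The late-cooling exclusion differs between 3.1 and 5.2 and must be reconciled.
- The main purpose in 9.1 and the Summary is ranked second in 2.0 and the Primary Objective, and has no measure in 2.1.
- The recruitment proportion has three wordings. With time-missed infants counted, the share by April 2013 is 68% or 50%, depending on whether about 7 or about 15 were missed and assuming no other losses. If all are dropped it is at most 100%.
- A predictor relation from 16 xenon infants is too imprecise to size a large trial. The figure of 6 to 8 positives assumes dichotomised predictors and positives about equal to poor outcomes.

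The documents do not show that the feasibility aim cannot be assessed, nor that the pilot's marker data are unfit as power inputs.

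**What to change.** 1. Reconcile the late-cooling exclusions in 3.1 and 5.2 with each other and with the eligibility box in 3.0. The choice is the sponsor's.
2. State one main purpose consistently in the Summary, 2.0, the Primary Objective, 2.1 and 9.1, and list the recruitment proportion among the endpoints.
3. Use one denominator in 2.0 and 3.3 that counts infants missed for time as not recruited. State how many were missed by April 2013, and report the proportion with an exact 95% interval. Reporting it before and after the transportable system is optional, where records allow.
4. Delete or limit the sample-size sentences in 3.2 and 7.5.4, and report the predictive value descriptively with an exact interval. Reason 3 in 3.3 can stay.

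**Cost.** Section 11.0 requires approval of an amendment by the ethics committee, MHRA, sponsor and investigators, with at least 15 of 32 infants already recruited. Screening records for infants missed earlier may be incomplete. The claim about the early predictors becomes weaker. Items 2 to 4 leave treatment, allocation and group size unchanged; item 1 may affect who can enter, depending on the cut-off chosen.
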